1. DIAGNOSIS VERSUS SIGNS AND SYMPTOMS

1.1. INJECTION-SITE REACTIONS

Adverse events that occur during or after study drug administration and are judged to be related to study treatment injection should be captured as a diagnosis (e.g., "ISR", "anaphylactic reaction") on the Adverse Event eCRF. If possible, avoid ambiguous terms such as "systemic reaction". Associated signs and symptoms should be recorded on the dedicated Injection Reaction eCRF. If a participant experiences both a local and systemic reaction to the same dose of study drug, each reaction should be recorded separately on the Adverse Event eCRF, with signs and symptoms also recorded separately on the dedicated Injection Reaction eCRF.

1.2. OTHER ADVERSE EVENTS

For adverse events other than injection reactions (see Section 1.1), a diagnosis (if known) should be recorded on the Adverse Event eCRF rather than individual signs and symptoms (e.g., record only liver failure or hepatitis rather than jaundice, asterixis, and elevated transaminases). However, if a constellation of signs and/or symptoms cannot be medically characterized as a single diagnosis or syndrome at the time of reporting, each individual event should be recorded on the Adverse Event eCRF. If a diagnosis is subsequently established, all previously reported adverse events based on signs and symptoms should be nullified and replaced by one adverse event report based on the single diagnosis, with a starting date that corresponds to the starting date of the first symptom of the eventual diagnosis.

2. ADVERSE EVENTS OCCURRING SECONDARY TO OTHER EVENTS

In general, adverse events occurring secondary to other events (e.g., cascade events or clinical sequelae) should be identified by their primary cause, with the exception of severe or serious secondary events. However, medically significant adverse events occurring secondary to an initiating event that are separated in time should be recorded as independent events on the Adverse Event eCRF. For example:

- If vomiting results in mild dehydration with no additional treatment in a healthy adult, only vomiting should be reported on the eCRF.
- If vomiting results in severe dehydration, both events should be reported separately on the eCRF.
- If a severe gastrointestinal hemorrhage leads to renal failure, both events should be reported separately on the eCRF.
- If dizziness leads to a fall and subsequent fracture, all three events should be reported separately on the eCRF.

All adverse events should be recorded separately on the Adverse Event eCRF if it is unclear as to whether the events are associated.

3. PERSISTENT OR RECURRENT ADVERSE EVENTS

A persistent adverse event is one that extends continuously, without resolution, between participant evaluation time-points. Such events should only be recorded once on the Adverse Event eCRF. The initial severity of the event should be recorded, and the severity should be updated to reflect the most extreme severity any time the event worsens. If the event becomes serious, the Adverse Event eCRF should be updated to reflect this.

A recurrent adverse event is one that resolves between participant evaluation time-points and subsequently recurs. Each recurrence of an adverse event should be recorded separately on the Adverse Event eCRF.

4. ABNORMAL LABORATORY VALUES

Not every laboratory abnormality qualifies as an adverse event. A laboratory test result should be reported as an adverse event if it meets any of the following criteria:

- Accompanied by clinical symptoms.
- Results in a change in study treatment (e.g., dosage modification, treatment interruption, or treatment discontinuation).
- Results in a medical intervention (e.g., potassium supplementation for hypokalemia) or a change in concomitant therapy.
- Clinically significant in the Investigator's judgment.

It is the Investigator's responsibility to review all laboratory findings. Medical and scientific judgment should be exercised in deciding whether an isolated laboratory abnormality should be classified as an adverse event.

If a clinically significant laboratory abnormality is a sign of a disease or syndrome (e.g., alkaline phosphatase and bilirubin 5 times the upper limit of normal [ULN] associated with cholecystitis), only the diagnosis (i.e., cholecystitis) should be recorded on the Adverse Event eCRF.

If a clinically significant laboratory abnormality is not a sign of a disease or syndrome, the abnormality itself should be recorded on the Adverse Event eCRF, along with a descriptor indicating if the test result is above or below the normal range (e.g., "elevated potassium", as opposed to "abnormal potassium"). If the laboratory abnormality can be characterized by a precise clinical term per standard definitions, the clinical term should be recorded as the adverse event. For example, an elevated serum potassium level of 7.0 mEq/L should be recorded as "hyperkalemia".

Observations of the same clinically significant laboratory abnormality from visit to visit should not be repeatedly recorded on the Adverse Event eCRF, unless the etiology changes. The initial severity of the event should be recorded, and the severity or seriousness should be updated any time the event worsens.

5. ABNORMAL VITAL SIGN VALUES

Not every vital sign abnormality qualifies as an adverse event. A vital sign result should be reported as an adverse event if it meets any of the following criteria:

- Accompanied by clinical symptoms.
- Results in a change in study treatment (e.g., dosage modification, treatment interruption, or treatment discontinuation).
- Results in a medical intervention or a change in concomitant therapy.
- Clinically significant in the Investigator's judgment.

It is the Investigator's responsibility to review all vital sign findings. Medical and scientific judgment should be exercised in deciding whether an isolated vital sign abnormality should be classified as an adverse event.

If a clinically significant vital sign abnormality is a sign of a disease or syndrome (e.g., high blood pressure), only the diagnosis (i.e., hypertension) should be recorded on the Adverse Event eCRF.

Observations of the same clinically significant vital sign abnormality from visit to visit should not be repeatedly recorded on the Adverse Event eCRF, unless the etiology changes. The initial severity of the event should be recorded, and the severity or seriousness should be updated any time the event worsens.

6. ABNORMAL LIVER TRANSAMINASES AND FUNCTION TESTS

The finding of an elevated ALT or AST ($> 3 \times \text{ULN}$ in healthy participants or $> 3x$ baseline in CHB patients) in combination with either an elevated total bilirubin ($> 2 \times \text{ULN}$) or clinical jaundice in the absence of cholestasis or other causes of hyperbilirubinemia is considered to be an indicator of severe liver injury. Therefore, investigators must report as an adverse event the occurrence of either of the following:

- Treatment-emergent ALT or AST $> 3 \times \text{ULN}$ (or $> 3x$ baseline) in combination with total bilirubin $> 2 \times \text{ULN}$.
- Treatment-emergent ALT or AST $> 3 \times \text{ULN}$ (or $> 3x$ baseline) in combination with clinical jaundice.
- Treatment-emergent ALT or AST $> 3 \times \text{ULN}$ (or $> 3x$ baseline) in combination with INR/PT > 1.5
- Treatment-emergent ALT or AST $> 3x \text{ ULN}$ (or $> 3x$ baseline) with the appearance of fatigue, nausea, vomiting, right upper quadrant abdominal pain or tenderness, fever, rash and/or eosinophilia.

The most appropriate diagnosis or (if a diagnosis cannot be established) the abnormal laboratory values should be recorded on the Adverse Event eCRF and reported to the Sponsor immediately (i.e., no more than 24 hours after learning of the event), either as a serious adverse event or a non-serious adverse event of special interest (see Section [8.3.6](#)).

7. DEATHS

All deaths that occur during the protocol-specified adverse event reporting period (see Section 5 of [Appendix 2](#)), regardless of relationship to study treatment, must be recorded on the Adverse Event eCRF and immediately reported to the Sponsor. This includes death attributed to progression of CHB.

Death should be considered an outcome and not a distinct event. The event or condition that caused or contributed to the fatal outcome should be recorded as the single medical concept on the Adverse Event eCRF. Generally, only one such event should be reported. If the cause of death is unknown and cannot be ascertained at the time of reporting, “unexplained death” should be recorded on the Adverse Event eCRF. If the cause of death later becomes available (e.g., after autopsy), “unexplained death” should be replaced by the established cause of death. The term “sudden death” should not be used unless combined with the presumed cause of death (e.g., “sudden cardiac death”).

8. PREEXISTING MEDICAL CONDITIONS

A preexisting medical condition is one that is present at the screening visit for this study. Such conditions should be recorded on the General Medical History and Baseline Conditions eCRF.

A preexisting medical condition should be recorded as an adverse event only if the frequency, severity, or character of the condition worsens during the study. When recording such events on the Adverse Event eCRF, it is important to convey the concept that the preexisting condition has changed by including applicable descriptors (e.g., “more frequent headaches”).

9. WORSENING OF CHB

Lack of RO7239958 efficacy in terms of changes in HBsAg does not qualify for adverse event in Part 2 of this study.

Medical occurrences or symptoms of deterioration in a course of chronic HBV infection should be recorded as adverse events if judged by the Investigator to have unexpectedly worsened in severity or frequency or changed in nature at any time during the study.

Virological breakthrough (HBV DNA rebound) and abnormal liver function tests (total bilirubin > 2x ULN, INR/PT > 1.5) should be reported as adverse events.

Medical occurrences or symptoms of deterioration that are anticipated as part of chronic HBV infection should be recorded as an adverse event if judged by the Investigator to have unexpectedly worsened in severity or frequency or changed in nature at any time during the study. When recording an unanticipated worsening of CHB on the Adverse Event eCRF, it is important to convey the concept that the condition has changed by including applicable descriptors (e.g., “worsening of CHB”).

10. HOSPITALIZATION OR PROLONGED HOSPITALIZATION

Any adverse event that results in hospitalization or prolonged hospitalization should be documented and reported as a serious adverse event (per the definition of serious adverse event in [Appendix 2](#)), except as outlined below.

An event that leads to hospitalization under the following circumstances should not be reported as an adverse event or a serious adverse event:

- Hospitalization for respite care
- Planned hospitalization
- Hospitalization for a preexisting condition, provided that all of the following criteria are met:

The hospitalization was planned prior to the study or was scheduled during the study when elective surgery became necessary because of the expected normal progression of the disease.

The participant has not suffered an adverse event.

An event that leads to hospitalization under the following circumstances is not considered to be a serious adverse event, but should be reported as an adverse event instead:

- Hospitalization for an adverse event that would ordinarily have been treated in an outpatient setting had an outpatient clinic been available.

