1. DEFINITION OF ADVERSE EVENTS

According to the E2A ICH guideline for Good Clinical Practice, an **adverse event** is any untoward medical occurrence in a patient or clinical investigation subject administered a pharmaceutical product and which does not necessarily have to have a causal relationship with this treatment.

An adverse event can therefore be:

- Any unfavorable and unintended sign (including an abnormal laboratory finding), symptom, or disease temporally associated with the use of a medicinal product, whether or not considered related to the medicinal product.

Events Meeting the AE Definition:

- Any deterioration in a laboratory value (hematology, clinical chemistry, or urinalysis) or other clinical test (e.g., ECG, X-ray) that is associated with symptoms or leads to a change in study treatment or concomitant treatment or discontinuation from study treatment.
- Exacerbation of a chronic or intermittent pre-existing condition, including either an increase in frequency and/or intensity of the condition.
- New conditions detected or diagnosed after study treatment administration even though it may have been present before the start of the study.
- Adverse events that are related to a protocol-mandated intervention, including those that occur prior to assignment of study treatment (e.g., screening invasive procedures such as biopsies).
- "Lack of efficacy" or "failure of expected pharmacological action" per se will not be reported as an AE or SAE. Such instances will be captured in the efficacy assessments. However, the signs, symptoms, and/or clinical sequelae resulting from lack of efficacy will be reported as AE or SAE if they fulfill the definition of an AE or SAE.

Events NOT Meeting the AE Definition (for Part 1):

- Any clinically significant abnormal laboratory findings or other abnormal safety assessments, unless judged by the Investigator to be more severe than expected for the participant's condition.
- Medical or surgical procedure (e.g., endoscopy, appendectomy): the condition that leads to the procedure is an AE.
- Situations where an untoward medical occurrence did not occur (social and/or convenience admission to a hospital).

- Anticipated day-to-day fluctuations of pre-existing disease(s) or condition(s) present or detected at the start of the study that do not worsen.

Events NOT Meeting the AE Definition (for Part 2):

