2. DEFINITION OF SERIOUS ADVERSE EVENTS

If an event is not an AE per definition above, then it cannot be a serious adverse event (SAE) even if serious conditions are met (e.g., hospitalization for signs/symptoms of the disease under study, death due to progression of disease).

A serious adverse event is defined as any untoward medical occurrence that at any dose:

- **Results in death.**
- **Is life-threatening.**
The term "life-threatening" in the definition of "serious" refers to an event in which the participant was at risk of death at the time of the event; it does not refer to an event which hypothetically might have caused death if it was more severe.
- **Requires inpatient hospitalization or prolongation of existing hospitalization** (see [Appendix 3](#)).

In general, hospitalization signifies that the participant has been detained (usually involving at least an overnight stay) at the hospital or emergency ward for observation and/or treatment that would not have been appropriate in the physician's office or outpatient setting. Complications that occur during hospitalization are AEs. If a complication prolongs hospitalization or fulfills any other serious criteria, the event is serious. When in doubt as to whether "hospitalization" occurred or was necessary, the AE should be considered serious.

Hospitalization for elective treatment of a pre-existing condition that did not worsen from baseline is not considered an AE.

- **Results in persistent or significant disability/incapacity**

Disability means substantial disruption of the participant's ability to conduct normal life functions.

This definition is not intended to include experiences of relatively minor medical significance such as uncomplicated headache, nausea, vomiting, diarrhea, influenza, and accidental trauma (e.g., sprained ankle) which may interfere with or prevent everyday life functions but do not constitute a substantial disruption.

- **Is a congenital anomaly/birth defect.**

- **Other significant events:**

Medical or scientific judgment should be exercised in deciding whether SAE reporting is appropriate in other situations such as important medical events that may not be immediately life-threatening or result in death or hospitalization but may jeopardize the participant or may require medical or surgical intervention to prevent one of the other outcomes listed in the above definition. These events should usually be considered serious.

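### Appendix 3 Section 10 exempts any planned hospitalization from AE and SAE reporting without a condition, which contradicts the reporting rules in Section 8.3.1 and Appendix 2

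*Combined protocol and SAP*

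**What the plan says.** Appendix 3 Section 10 first makes any AE that results in hospitalization an SAE, subject to exceptions. The first group of exceptions opens with: "An event that leads to hospitalization under the following circumstances should not be reported as an adverse event or a serious adverse event". Three circumstances follow:

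- respite care;
- "Planned hospitalization", with nothing further;
- "Hospitalization for a preexisting condition, provided that all of the following criteria are met". The criteria concern when the admission was arranged and why, and include "The participant has not suffered an adverse event".

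A separate closing paragraph deals with admissions that are AEs but not SAEs.

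Other parts of the protocol set different rules for the same situation:

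- Section 8.3.1: after the first dose every AE is reported, whatever its cause, until 105 days after the last dose. No exception is made for hospitalization.
- Appendix 2 Section 1: a condition first found after dosing is an AE. For medical or surgical procedures, in both study parts, "the condition that leads to the procedure is an AE".
- Appendix 2 Section 2: "Hospitalization for elective treatment of a pre-existing condition that did not worsen from baseline is not considered an AE".
- Appendix 3 Section 8: "A preexisting medical condition should be recorded as an adverse event only if the frequency, severity, or character of the condition worsens during the study".

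**The concern.** The lead-in removes the event itself from reporting, not only the admission. Because the second bullet has no qualifier, a site could apply it to a condition that arose on treatment and was then managed by a booked admission. Whether such an event is recorded could then depend on whether the admission was scheduled or urgent.

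The incidence, severity and causality of AEs form one component of the primary endpoint (Section 3, Table 7). Hospitalization is also an SAE criterion, and SAEs must reach the sponsor within 24 hours (Appendix 2 Section 5). Appendix 2 Section 2 adds that something which is not an AE cannot be an SAE, so a site that applies the bullet loses both reports at once.

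Sites are sent to this text. Section 8.3 refers to Appendix 3 for the recording procedures and lists hospitalization among them, and the hospitalization criterion in Appendix 2 Section 2 also points to Appendix 3.

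**Working it through.** The plan gives no figure to reproduce here: Section 9.1 plans no hypothesis tests and Section 9.2 has no power calculation. The check is a comparison of the texts, followed by simple arithmetic on group sizes.

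**Step 1: does the lead-in cover AEs as well as SAEs?** Yes. It names both, and Section 10 uses a separate paragraph where it means AE but not SAE.

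**Step 2: do the third bullet's conditions also govern the second?** No. They are tied to the third bullet by its own wording, "Hospitalization for a preexisting condition, provided that all of the following criteria are met". The third bullet covers admissions planned before the study or scheduled during it for an elective reason. Both are planned admissions, so every case that satisfies the third bullet already satisfies the second. Read literally, the second bullet makes the third bullet's conditions redundant.

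**Step 3: apply each text to the same cases.**

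| Case | Appendix 3 Section 10, second bullet read literally | Other text |
|---|---|---|
| New condition after first dose, admission booked for a procedure | Not reported | AE under Appendix 2 Section 1; reportable under Section 8.3.1; outside the Appendix 2 Section 2 exemption because it is not pre-existing |
| Pre-existing condition that worsens after first dose, elective admission booked | Not reported | AE under Appendix 3 Section 8; outside the Appendix 2 Section 2 exemption because it worsened |
| Pre-existing condition, unchanged, admission planned before the study | Not reported | Not an AE under Appendix 2 Section 2 |
| New condition, emergency admission | Bullet does not apply | AE, and an SAE by the hospitalization criterion |

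The texts agree in the last two cases and contradict each other in the first two. No section states an order of precedence.

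**Step 4: what one omitted event would do.** Inputs (Section 9.2): 8 active participants per Part 1 cohort and 6 per Part 2 arm. Formula: change in observed incidence = 1/n.

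- Part 1 cohort: 1/8 = 12.5 percentage points.
- Part 2 arm: 1/6 = 16.7 percentage points.

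These shifts in AE incidence arise only if the participant has no other recorded AE; otherwise the participant is already counted and the shift is zero. For SAE incidence the same condition applies with SAE in place of AE. The denominators are nominal: Section 5.5 allows up to two extra patients per Part 2 arm, and Sections 7.1 and 7.2 allow some replacement.

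**Step 5: how often?** The documents give no rate of scheduled admissions and no basis for one, so no expected number of lost events can be calculated.

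**The case against.** The strongest reply is that the event remains reportable whatever the bullet says. Section 8.3.1 and Appendix 2 Section 1 require it, and a site that recorded nothing would breach both. Appendix 2 Section 3.1 also makes Grade 4 and 5 events SAEs without regard to how an admission was arranged. The toxicities this study anticipates have their own routes: liver events are reported within 24 hours under Section 8.3.6 and Appendix 3 Section 6, and liver and eGFR findings have stopping criteria in Section 4.1.3. Injection site reactions and scheduled laboratory, ECG, vital-sign and physical findings are separate items of the primary endpoint.

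Most of this stands, and it limits the point. A reader might infer that any such event definitely drops out of the primary safety endpoint. The documents do not support that: the outcome depends on which text a site follows, and only AE reporting is exposed. The reply does not remove the contradiction, because Appendix 3 is the place to which sites are directed for recording hospitalizations and nothing subordinates it to the other sections.

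A reader might also infer that the third bullet is faulty because it covers an admission "scheduled during the study when elective surgery became necessary because of the expected normal progression of the disease". That does not hold. All of the bullet's criteria must be met, including "The participant has not suffered an adverse event", and under Appendix 3 Section 8 a worsened pre-existing condition is an AE, so the exemption fails in that case. For chronic hepatitis B, the reference to expected progression also agrees with the Part 2 list in Appendix 2 Section 1 and with Appendix 3 Section 9.

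**Conclusion.** Wrong as written: the second bullet of Appendix 3 Section 10 contradicts Section 8.3.1 and Appendix 2 Sections 1 and 2, and for worsened pre-existing conditions it also contradicts Appendix 3 Section 8. A treatment-emergent event with a scheduled admission could go unreported, and sites could differ on the AE component of the primary endpoint and on 24-hour SAE reporting.

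The practical effect is probably small. It is confined to scheduled admissions, and its frequency cannot be derived from the documents. The shifts of 12.5 and 16.7 points assume nominal active groups of 8 and 6 and a participant with no other recorded AE. They show how sensitive small groups are to one missing report and do not estimate the loss. The third bullet is sound and is not part of this conclusion.

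**What to change.** Replace the second bullet with: hospitalization planned before informed consent, or an in-clinic stay required by this protocol. Add one sentence saying that the exemption covers the admission only, and that any new or worsened condition leading to it is recorded as an AE, and as an SAE where it meets the criteria. This brings Section 10 into line with Section 8.3.1, Appendix 2 Sections 1 and 2, and Appendix 3 Section 8. Leave the third bullet as it is.

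The cost is one wording change in Appendix 3, a short note to sites, and possibly a few more AE or SAE reports. Design, sample size and analysis do not change.
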